### 10.1.2 Sensitivity Analyses

A sensitivity analysis will be performed using descriptive summary statistics for the primary effectiveness endpoint but based on the observed data in the Implanted Population.

Another sensitivity analysis will be performed to assess the impact of missing data on the primary effectiveness analysis. Multiple imputation (van Buuren 2007) will be used for missing IOP data for patients lost to follow-up prior to Month 12 (see sample SAS code below). The worst observation carried forward (WOCF) method will be used to impute missing IOP data following non-study surgical procedures for IOP control or device explant and missing concomitant IOP-lowering medication counts.

```
proc mi data=eff out=mi seed=123456 nimpute=20;
  where eos='lost to follow-up';
  class sex race;
  fcs nbiter = 100 reg(/details);
  var iop12 iop10 iop08 iop06 iop03 iop01 iopb medcntb age sex race;
run;
```

The imputed IOP and/or medication counts will be used to derive the missing binary outcomes for the primary effectiveness analysis. The estimation of proportion and the standard error of the estimation will be calculated for each imputation based on primary analysis model:

```
proc genmod data=mi(where=(visit gt 0)) descending;
  by _imputation_;
  class visit pid;
  model resp=bliop visit/link=logit dist=bin;
  repeated subject=pid/type=un within=visit;
  lsmeans visit/cl alpha=0.05;
  ods output lsmeans=lsms(keep=visit estimate lower upper);
run;
```

PROC MIANALYZE procedure available in SAS software will be used to combine results and generate the overall estimate and corresponding 2-sided 95% CI; see sample SAS code below:

```
proc mianalyze data=lsms;
  modeffects prop;
  stderr prop_se;
  ods output parameterestimates=miresult;
run;
```

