6.4 Early Discontinuation of Patients

Each patient reserves the right to withdraw from the study at any time without jeopardy to his/her future medical care. In addition, patients meeting withdrawal criteria (Section 6.5) will be discontinued from the study. All follow-up assessments and procedures are to be performed at the final study visit. Patients may also be administratively withdrawn if they do not return for follow-up visits.

For any patient who withdraws from the study, the date and reason for withdrawal will be recorded on the eCRF. If an AE is ongoing at the time of withdrawal, the investigator will attempt to follow the patient until the AE has been resolved or follow-up is no longer possible. The investigator shall ask for the patient's permission to follow his/her status/condition outside the study.

If a patient fails to return for one or more scheduled study visits, the investigator will attempt to contact the patient to determine and document the reason the patient has failed to return and to encourage compliance with the study visit schedule.

Notification of early patient discontinuation from the study and the reason for discontinuation will be made to the sponsor and clearly documented on the appropriate eCRF.

When a patient discontinues or withdraws from the study before 12 months, every effort should be made to have these patients return to the clinical center to complete the procedures for the early exit visit.

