6.5 Withdrawal Criteria

Patients may voluntarily withdraw from the study at any time.

Patients who have their devices removed or have a suture placed to close the scleral channel, will be withdrawn from the study.

Patients who are not implanted with XEN during surgery will be withdrawn from the study and considered a screen failure. Investigators are recommended to follow the patient until they are stable.

The investigator will consider withdrawing a patient from the study early if any of the following criteria are met:

- Patient develops (or has an exacerbation of) a medical condition that, in the opinion of the investigator, compromises the patient's ability to participate in the study
- Patient is unwilling or unable to continue to comply with study procedures
- Patient is unwilling or unable to continue in the study

Whenever possible, the decision to withdraw a patient from the study or study treatment will be discussed with the sponsor.

7. Response Measures and Summary of Data Collection Methods

Detailed information on equipment and methodology to be used is provided in the Protocol Procedure Manual.

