## **7.0            PATIENT DISPOSITION**

Number and percent of patients who entered and completed the screening phase and who failed during the screening phase further broken down by most important failed criterion collected on the screening disposition electronic case report form (eCRF) and timing of failure collected on the subject qualification eCRF will be tabulated for all screened patients. Failed criteria include ‘Screen Failure’, ‘Adverse Event’, ‘Withdrawal by subject’, ‘Lost to Follow-Up’, ‘Pregnancy’, ‘Death’, ‘Physician decision’, ‘Protocol Deviation’, ‘Study Terminated by the Sponsor’, ‘Site Terminated by the Sponsor’ and ‘Other’. Under ‘Screen Failure’, timing of failure and inclusion/exclusion criterion not met will be presented.

Disposition summary tables for patients in the Implanted Population will be presented for study and study treatment. These tables will summarize the number and percent of patients who completed the study/study treatment and discontinued pre-maturely from study/study treatment further broken down by most appropriate reason for discontinuation as collected on the follow-up disposition and device complaint eCRF. Reasons for pre-mature discontinuation from the study include ‘Adverse Event’, ‘Withdrawal by subject’, ‘Lost to Follow-Up’, ‘Pregnancy’, ‘Death’, ‘Physician decision’, ‘Protocol Deviation’, ‘Study Terminated by the Sponsor’, ‘Site Terminated by the Sponsor’, ‘Technical Problems’, and ‘Other’. Reasons for pre-mature discontinuation from the study treatment include ‘Persistent hypotony that cannot be mitigated by other means’, ‘Uveitis, glaucoma and hyphema syndrome’, ‘Gross device malposition’, ‘Surgical procedure that requires explant (eg, trabeculectomy)’, and ‘Other’.

Study exit status will also be listed for all screened patients.

In addition, enrollment by region (Asia-Pacific, other) and study site will also be summarized in the Implanted Population.

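### The missing-data sensitivity analysis has no IOP rule for patients who exit for reasons other than loss to follow-up, explant or IOP surgery

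*SAP*

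**What the plan says.** The primary analysis (SAP 10.1.1) is a repeated-measures logistic model fitted in PROC GENMOD without imputation. SAP 10.1.2 adds two sensitivity analyses. One is a descriptive summary of observed data. The other is intended to show how far missing data could affect the primary result, and it has two rules for missing IOP:

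- Multiple imputation: "Multiple imputation (van Buuren 2007) will be used for missing IOP data for patients lost to follow-up prior to Month 12". The sample PROC MI code carries the condition "where eos='lost to follow-up".
- WOCF, used to "impute missing IOP data following non-study surgical procedures for IOP control or device explant and missing concomitant IOP-lowering medication counts".

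SAP 7.0 shows what the exit-reason field can contain: "Reasons for pre-mature discontinuation from the study include ‘Adverse Event’, ‘Withdrawal by subject’, ‘Lost to Follow-Up’, ‘Pregnancy’, ‘Death’, ‘Physician decision’, ‘Protocol Deviation", followed by study or site termination by the sponsor, technical problems and other, making 11 reasons.

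Protocol 6.5 adds a compulsory exit: "Patients who have their devices removed or have a suture placed to close the scleral channel, will be withdrawn from the study". The sample-size sections (Protocol 8.5, SAP 14.0) plan 65 implanted patients so that at least 50 have 12 months of follow-up, and state a precision of ±0.145.

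**The concern.** An analysis meant to test the effect of missing data should reach every patient whose Month 12 response is missing. This one reaches two groups. A patient who exits under another SAP 7.0 reason, with neither explant nor non-study IOP surgery, gets no IOP value. Without IOP the responder variable cannot be derived, so that patient's Month 12 response is missing in the sensitivity analysis exactly as in the primary.

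The primary is a GEE fit, which in general relies on dropout not depending on outcome given the covariates. Exits for adverse events or by physician decision are where that assumption is least secure. If they are missing from both analyses, agreement between the two is partly built in. The trial tests no hypothesis, and its main output is one proportion with its interval, so what is at stake is how much confidence that proportion deserves.

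**Working it through.** **Does any rule reach these patients?**

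| Analysis | Missing Month 12 IOP after exit for, say, an adverse event, with no explant or IOP surgery |
|---|---|
| Primary (SAP 10.1.1) | not imputed |
| Observed-data summary (SAP 10.1.2) | not imputed |
| Multiple imputation (SAP 10.1.2) | excluded by prose and by the exit-reason condition |
| WOCF (SAP 10.1.2) | does not apply to their IOP; applies to their medication count |

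An early exit visit does not usually supply the value. SAP 16.1 assigns visits by study day, and Month 12 starts at Day 336; an exit visit on Day 200 falls in the Month 6 window (Days 138 to 213).

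**The plan's own figure.** For x responders among n = 50, the exact 95% limits are the 0.025 quantile of Beta(x, n − x + 1) and the 0.975 quantile of Beta(x + 1, n − x). The widest interval is at x = 25: 0.3553 to 0.6447, half-width 0.1447. The stated 0.145 is reproduced.

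**Inputs for the size.**
- Without Month 12 data: 65 − 50 = 15, and 15/65 = 23.1% (Protocol 8.5, SAP 14.0). This is the most the plan's own target allows for.
- Response rate: 76%, from the earlier refractory-glaucoma study in Protocol 2.1. It is assumed here for the 50 observed (38 responders) and for any imputed patient.
- m: the patients among the 15 whom neither IOP rule reaches. The documents do not give it.

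**Formulas.** These are simple proportions, not GEE estimates.
- As written: 0.76 × (65 − m) / (65 − m) = 76%, whatever m is.
- All m count as failures: 0.76 × (65 − m) / 65.
- All m count as responders: [0.76 × (65 − m) + m] / 65.
- Shift from 76%: down 0.76m/65, up 0.24m/65; full range m/65.

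| m | As written | All fail | All respond | Down / up (points) |
|---|---|---|---|---|
| 5 | 45.6/60 = 76% | 45.6/65 = 70.2% | 50.6/65 = 77.8% | 5.8 / 1.8 |
| 10 | 41.8/55 = 76% | 41.8/65 = 64.3% | 51.8/65 = 79.7% | 11.7 / 3.7 |
| 15 | 38/50 = 76% | 38/65 = 58.5% | 53/65 = 81.5% | 17.5 / 5.5 |

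The downward shift passes 14.5 points only when m exceeds 0.145 × 65 / 0.76 = 12.4, that is, from m = 13.

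**A benchmark for m.** In the earlier study (Protocol 2.1), 52 of 65 had Month 12 medication data, so 13 did not, and 13.8% (about 9 of 65) needed secondary surgery. The overlap is not reported. If all 9 were among the 13, about 4 remain for loss to follow-up and every other reason together. At m = 4 the bounds are 0.76 × 61/65 = 71.3% and 71.3% + 4/65 = 77.5%.

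**The case against.** The strongest reply is that the clearest outcome-linked exits are already handled. Explant forces withdrawal, and IOP missing after explant or further IOP surgery goes to WOCF whatever exit reason is recorded, so some adverse-event exits are covered. Several remaining reasons, such as pregnancy or site termination, have no obvious link to outcome. The benchmark above suggests that m may be small. All of this stands: it limits the size of the gap but does not close it.

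It could also be said that loss to follow-up is loose wording for any dropout. The code condition and the separate SAP 7.0 category point to the narrow meaning. Protocol 6.4 does say "Patients may also be administratively withdrawn if they do not return for follow-up visits"; that is ordinary loss to follow-up and is not part of the gap.

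Stronger readings are tempting and should not be drawn:

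- *That imputing these patients would move the result to 64% or 80%.* Those are all-fail and all-respond bounds. Imputing all 15 at 76% gives (38 + 11.4)/65 = 76%. Imputation that assumes missingness at random need not reveal outcome-linked dropout, so a bounding case is needed as well.
- *That the 15-point range at m = 10 equals the planned precision.* That sets a full range against a half-width. The shifts from 76% are 11.7 points down and 3.7 up.
- *That nothing is imputed for these patients.* Missing medication counts are carried forward whatever the exit reason; only IOP has no rule.
- *That suture withdrawals are certainly left out.* Protocol 6.5 names the suture separately from device removal, but SAP 10.0 identifies non-study IOP procedures through a look-up table still to be supplied. Protocol 8.2.3 defers the device-failure definition to the analysis plan, and no text is visible under SAP 10.3. The question is open.
- *That completers who miss Month 12 form a sizeable further group.* Patients exit on completing that visit (Protocol 6.1.5), and its analysis window has no upper limit (SAP 16.1), so this group is nearly empty.

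**Conclusion.** The point holds for IOP. By both prose and code, SAP 10.1.2 leaves some exits without a Month 12 response, so it cannot fully assess the effect of missing data. On the assumptions shown, the bounds it fails to display are about 70% to 78% for m = 5 and 64% to 80% for m = 10, and narrower if many of the 15 are device failures under WOCF. The size rests on an unknown m and an assumed 76%. If WOCF patients respond less often than 76%, the bounds move down but the range m/65 does not change. This is a supportive analysis in an estimation study, so the primary estimate is unaffected. The flaw is that a stated check does not do what it is there for, and it is cheap to correct.

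**What to change.** In SAP 10.1.2:

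1. Remove the exit-reason condition from PROC MI, so that the imputation model is fitted on the whole Implanted Population. Widening it only to other non-completers would not work, because they have little or no observed Month 12 IOP from which to estimate the model.
2. Impute missing Month 12 IOP for every implanted patient without it, whatever the disposition reason. Keep WOCF for device failures and say that it takes precedence over the multiply imputed value.
3. Add a bounding case in which the exits that neither current IOP rule reaches count as non-responders.
4. State whether withdrawal for a scleral-channel suture is handled as a device failure in this analysis.

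The cost is a few SAP sentences and a changed selection condition. It needs no new data and does not change the primary analysis. The downside is a slightly wider and possibly less favourable sensitivity interval.

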6.1.3.2.3 Device Explant

XEN may be removed if the investigator believes that it is in the best interest of the patient. Device removal may be considered in the following situations:

- Persistent hypotony that cannot be mitigated by other means (see Section [6.1.3.2.1](#))
- Uveitis, glaucoma and hyphema syndrome
- Gross device malposition

- Surgical procedure that requires explant (eg, trabeculectomy)

Investigators will make all efforts to notify the sponsor prior to explantation of the device.

For explantation of XEN, the following will be considered:

- Implant removal through the conjunctiva:

A small (1 to 2 mm) conjunctival incision is made near the distal end of the implant. Using forceps, slowly remove the implant out of the eye. Investigator's discretion will be used to close the conjunctival wound.

- Implant removal from the anterior chamber:

A small (1 to 2 mm) incision is created to enter the anterior chamber. After using appropriate methods to maintain the anterior chamber shape (eg, injection of viscoelastic), forceps can be used to remove the implant from the eye. Investigator's discretion will be used in the method for closure of the corneal incision.

All device explants will be considered device failures. Patients who have their devices removed will be withdrawn from the study. These patients will be followed until the patient is deemed stable by the investigator. Examinations may be performed as necessary to ensure the safety and wellbeing of patients during the study period.

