### **3.0 LIST OF ABBREVIATIONS**

AC	anterior chamber
ACG	angle closure glaucoma
AE	adverse event
BCVA	Best-corrected visual acuity
eCRF	electronic case report form
IEAE	implant emergent adverse event
IOP	Intraocular pressure
K-M	Kaplan-Meier
MMRM	mixed-effects model for repeated measures
MSP	medical safety physician
NA	not applicable
OD	right eye
OS	left eye
OU	both eyes
PID	patient identification
PT	preferred term
SADE	serious adverse device effect
SAE	serious adverse event
SAP	statistical analysis plan
SE	study eye
SI	Le Système International d'Unités (International System of Units)
SOC	system organ class
TEAE	treatment-emergent adverse event
WOCF	worst observation carried forward

---

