### **10.0 EFFECTIVENESS ANALYSES**

The primary effectiveness measure is based on IOP measurements at post-baseline visits and number of IOP-lowering medications taken during post-baseline visits (see section 16.1 for more details). Any IOP measurements collected following non-study surgical procedures for IOP control or device explant (i.e., device failures) will be excluded from the analyses. Any medications taken following non-study surgical procedures for IOP

control will be excluded when determining the number of IOP-lowering medications. A look-up table of MedDRA terms to identify non-study surgical procedures for IOP control will be provided by the study MSP.

No formal statistical hypothesis will be tested.

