## **10.1 PRIMARY EFFECTIVENESS ASSESSMENTS**

### **10.1.1 Primary Analysis**

The primary effectiveness analysis will estimate the proportion of patients, with corresponding 2-sided 95% CI, that achieve at least a 20% reduction from baseline Hour 0 IOP while on the same number or fewer IOP-lowering medications at Month 12 compared with baseline using a mixed-effects repeated measures logistic regression model. The model will include visit as a fixed effect and baseline IOP as a covariate for repeated measures at Month 1, 3, 6, 8, 10, and 12. An unstructured covariance matrix will be used for repeated measures on the same patient; if the model with unstructured covariance fails to converge, an alternative covariance structure will be chosen. The Hour 0 IOP percent change from baseline at a timepoint is calculated as:

$$100 \times (\text{Timepoint Hour 0 IOP} - \text{Baseline Hour 0 IOP}) / \text{Baseline Hour 0 IOP}$$

First, a response variable will be derived from the effectiveness variables: Hour 0 IOP percent change from baseline and the number of concomitant IOP-lowering medications. If the percent change in Hour 0 IOP from baseline is less than or equal to  $-20\%$  at an analysis timepoint of interest **and** the number of IOP-lowering medications taken at the that timepoint is same or fewer compared to that at baseline, the response variable will be coded to value 1 and 0 otherwise. Refer to Section 8.4.2 for a discussion on determining the number of IOP-lowering medications taken at a timepoint of interest. GENMOD procedure available in SAS software will be used to fit the repeated measures logistic regression model; see sample SAS code below:

```
proc genmod data=one(where=(visit gt 0)) descending;
  class visit pid;
  model resp=bliop visit/link=logit dist=bin;
  repeated subject=pid/type=un within=visit;
  lsmeans visit/cl alpha=0.05;
  ods output lsmeans=lsms(keep=visit estimate lower upper);
run;
```

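### The missing-data sensitivity analysis derives a device failure's Month 12 response from an undefined WOCF value, so an explanted or re-operated eye can be scored as a success

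*SAP*

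**What the plan says.** Protocol 6.1.3.2.3 is categorical: "All device explants will be considered device failures". Its listed reasons for removal include "Persistent hypotony that cannot be mitigated by other means", and it withdraws the patient from the study after removal. SAP 10.0 adds: "Any IOP measurements collected following non-study surgical procedures for IOP control or device explant (i.e., device failures) will be excluded from the analyses". Only readings from before the failure therefore remain usable.

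The primary model (SAP 10.1.1) leaves the later visits missing. The second sensitivity analysis (SAP 10.1.2) fills them: the WOCF "method will be used to impute missing IOP data following non-study surgical procedures for IOP control or device explant". It continues: "The imputed IOP and/or medication counts will be used to derive the missing binary outcomes for the primary effectiveness analysis".

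The response rule in SAP 10.1.1 has two parts. The IOP part begins "If the percent change in Hour 0 IOP from baseline is less than or equal to" and sets the limit at minus 20%. The medication part requires that "the number of IOP-lowering medications taken at the that timepoint is same or fewer compared to that at baseline". There is no lower IOP limit and no device-failure condition.

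On WOCF itself, SAP 3.0 gives only the expansion "worst observation carried forward". The SAP text available does not say whether worst means highest, which visits are eligible, or whether baseline is one of them.

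**The concern.** By Month 12 the failure is a known fact, yet it is not an input to the outcome. The inputs are pressures and medication counts recorded while the device was still in place, or before the further surgery. Carrying forward a high pressure is a hard test when the device failed through high pressure. It is no test when the device was removed for over-drainage, malposition or inflammation while pressure was low, or when the eye was re-operated because it missed a target though still 20% below baseline.

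The stated purpose of this analysis is to assess the effect of missing data on the primary result. The primary model leaves device failures missing after the event, and the other sensitivity analysis uses observed data only. In the text available, this is the one analysis that gives these eyes a Month 12 outcome. If it can count some of them as responders, it tests the primary result less severely than it appears to.

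**Working it through.** **The plan's own figure.** SAP 14.0 states a precision of 0.145 with 50 patients. The largest exact Clopper-Pearson half-width for n = 50 occurs at 25/50, with limits 0.3553 and 0.6447: (0.6447 - 0.3553)/2 = 0.1447. The figure reproduces, and this point does not affect it.

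**Inputs from the documents.** Baseline IOP is 20 to 35 mm Hg (Protocol 5.3), so the success cut-off, 0.8 x baseline, is 16 to 28 mm Hg. Hypotony is IOP below 6 mm Hg (Protocol 4.4.1.1). IOP-lowering medications are suspended on the day of surgery (Protocol 4.4.2), so a hypotonous eye is likely, by inference, to meet the medication condition.

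**Deterministic cases.** Change = 100 x (imputed - baseline)/baseline; response is 1 if the change is -20% or lower and the medication condition is met.

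| Value carried forward | Baseline 20 | Baseline 35 |
|---|---|---|
| 5.9 (hypotony throughout) | -70.5%, coded 1 | -83.1%, coded 1 |
| 15 | -25.0%, coded 1 | -57.1%, coded 1 |
| 17 | -15.0%, coded 0 | -51.4%, coded 1 |
| 30 | +50.0%, coded 0 | -14.3%, coded 0 |
| Baseline itself | 0%, coded 0 | 0%, coded 0 |

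The first row is coded 1 whether worst means highest or lowest, because every post-operative reading is low. If baseline is eligible and worst means highest, the carried value is at or above baseline and every failure is coded 0. The same eye is thus a success or a failure depending on a choice the SAP does not record.

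**Probability of being coded a responder.** Assumptions: baseline normal with mean 25.1 and SD 3.7 (the earlier US trial, Protocol 2.1), truncated to 20-35; between-patient SD 1.5-3; between-visit SD 2-4; WOCF is the maximum of 3 to 7 post-operative readings; medication condition met. Only the baseline figures come from the documents. By simulation, with 200,000 eyes per scenario:

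| Mean post-operative IOP (mm Hg) | Coded responder |
|---|---|
| 5-8 | 94-100% |
| 10 | 87-100% |
| 14 | 60-94% |
| 16 | 41-80% |

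For an eye sent to IOP surgery whose worst reading averages 22 to 24 mm Hg (SD 4), the chance is 38% to 23%. Most of these (62-77%) are coded 0.

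**Effect on the rate.** One eye is 1/65 = 1.54 points. Starting from an illustrative 49/65 = 75.4%, recoding one such eye gives 48/65 = 73.8%, and recoding three gives 46/65 = 70.8%.

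**Net direction.** Suppose 9 failures (13.8% of 65, the earlier trial's secondary-surgery rate) and 76% response in the other 56, which is 42.56 responders.
- All nine coded 0: 42.56/65 = 65.5%.
- All nine re-operated for IOP, 23-38% coded 1: (42.56 + 2.07)/65 to (42.56 + 3.42)/65 = 68.7% to 70.7%.
- Three low-pressure explants coded 1 and six re-operated: (42.56 + 3 + 1.38)/65 to (42.56 + 3 + 2.28)/65 = 72.2% to 73.6%.

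In these illustrations WOCF still lowers the rate from 76%, but by 2.4 to 7.3 points, where coding failures as 0 lowers it by 10.5.

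**The case against.** A reader might infer that every eye explanted for hypotony will be scored a success. The documents do not support that. WOCF is undefined, and a version that includes baseline gives 0 every time. Persistent hypotony as a removal reason also does not mean low pressure at every visit since surgery: with highest as worst, one earlier eligible reading above 80% of baseline is enough for 0.

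A reader might also infer that the analysis leaves the responder rate unchanged or raises it, and so merely confirms the primary result. That would need low-pressure explants to dominate the failures, and no figure in the documents suggests they will. Most eyes re-operated for IOP would still be coded 0.

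The number of affected eyes may be small. Protocol 2.1 reports that none of the 16 hypotony cases in the earlier US trial needed surgical intervention; the 13.8% with secondary surgery covers all reasons. Explants are also visible elsewhere: Kaplan-Meier time to explant (SAP 9.0), removal reasons (SAP 7.0) and adverse events leading to removal (SAP 11.1). Protocol 8.2.3 defers details of the device-failure definition to the analysis plan, and the content of SAP 10.3 is not shown, so related handling there cannot be ruled out.

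All of this limits the size and certainty of the point. It does not supply the missing rule: SAP 10.1.2 governs this analysis, and as written it derives the outcome from the imputed values alone.

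**Conclusion.** The point holds in a conditional form. With WOCF over post-baseline, pre-failure readings, a device failure as the protocol defines it can be scored as a Month 12 success. This is near certain for an eye with low pressure throughout, anywhere from likely to roughly even for explants at 14-16 mm Hg, and the less likely outcome for eyes re-operated for IOP. With baseline eligible and worst meaning highest, it cannot happen. The probabilities rest on assumed SDs and numbers of readings. The count of affected eyes is an assumption throughout, at 1.5 points of crude rate per eye.

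The primary estimate is untouched, and SAP 10.0 plans no hypothesis test. The sensitivity analysis may well lower the rate, but by less than it should. The change is worth making because the present rule can contradict the protocol's own label for these eyes, and because the result turns on an unrecorded programming choice.

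**What to change.** In SAP 10.1.2, replace WOCF for device failures with direct coding: for any patient with device explant or non-study surgery for IOP control, set resp = 0 at every analysis visit after the date of that event, including Month 12, whatever the earlier IOP or medication count. Keep imputation for the other missing data. Since WOCF would remain in use for missing medication counts, state there what worst means, which visits are eligible and whether baseline is among them.

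The cost is a sentence or two and a line of code, using event dates the plan already needs in order to exclude post-failure IOP. No new data are required. The downside is that the sensitivity estimate may be slightly less favourable.
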